The test of the primary hypothesis compares the treatments without adjustment for any covariates. The secondary analyses, particularly secondary analysis will confirm or not confirm the primary hypothesis by considering variations on the primary analysis including logistic regression models that adjust for covariates. We note that logistic regression analysis yields a treatment odds ratio rather than the difference between proportions. In this case, to carry out the non-inferiority test, we will estimate the difference between treatments by linking the odds ratio to the overall proportion of participants who have one or more gout flares.

In addition to testing the primary hypothesis, extensive descriptive analyses outlined in (BRDP) will compare treatments with respect to selected variables among the demographic, medical history, laboratory values, anthropomorphic, vital sign, quality-of-life, alternative outcome, and side effect variables. Simple unadjusted comparisons will apply Student's t-test to continuous variables, the Wilcoxon test to highly skewed continuous or ordinal variables and will apply the Chi-square test (or Fisher's exact test) to categorical variables.

Non-adherence

Of relevance to this study, observational studies have indicated relatively poor adherence in patients with gout (40, 87-90) However, Dalbeth et al. (91) found that higher doses of allopurinol were associated with sUA levels at target independent of adherence with treatment. Because all study participants will receive active therapies of proven efficacy for lowering sUA levels as well as prophylactic treatment of acute gout symptoms, compliance issues are expected to be minimal in this trial. Other studies in rheumatoid arthritis have shown that if patients are doing well, issues of poor treatment adherence are minimized (92).

Participant adherence to protocol-directed study treatment will be assessed via pill counts, prescription renewals, and participant interview. We will use the question and pill count data to determine if a participant took 80% or more of treatment medication. The per-protocol population will be defined as participants remaining on the same treatment throughout the entirety of the study with 80% adherence.

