Toxicity events include rises in sUA levels, adverse changes in serum creatinine, CBC, liver function tests (LFTs), blood pressure, and the incidence of skin rashes. The incidence of cardiovascular events of interest, with particular emphasis on cardiovascular and all-cause mortality, will also be included in this analysis. Within each Phase we will determine if the incidence of such events differs between treatments. In the Phase 3 analysis baseline covariates will include the summary of toxicity events during Phases 1 and 2 as well as the 48-week sUA level. As in the sixth secondary analysis the same statistical methods for Poisson counts will be used to express time-dependent events.

At each clinic visit we will assess the count of each type of major side effect episodes between visits. Deviations from the titration protocol will be modeled as a binary factor. We will model counts that have substantial variation as Poisson random variables. These outcome measures include each count and the aggregate count. These counts will be coarsened into binary outcomes of no events versus one or more events. The analyses will compare treatments using a longitudinal repeated measures analysis with Poisson count, negative binomial counts, and binary outcomes (PROC GLIMMIX and GENMOD in SAS). Missing data methods will address potential censoring of events among patients who fail to attend clinic visits. We will run this same analysis using the biological threshold of sUA <6.8 mg/dl after 48 weeks.

- 8) To describe the effects of baseline covariates and time-dependent covariates on the primary results.

Baseline data include demographic characteristics (e.g. age, sex), disease history including CKD level, presence of tophi at baseline, height, weight, laboratory values, medications, other comorbidities, and quality-of-life measures. Data obtained often after baseline include sUA values, titration levels, side effects, and gout flare counts. Many baseline measurements are repeated at 24 and 48 weeks. All data obtained before Phase 3 may be used as baseline factors for Phase 3 analyses such as the primary hypothesis and secondary object #1. Secondary analyses 2-7 can adjust for covariates obtained at baseline and at 24 weeks.

All major analyses will be repeated on the per-protocol population with adherence and non-adherence as defined above. The objective is to either confirm our results or detect that adherence to treatment alters the result.

Missing Data

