### 5.3. Univariate and Bivariate Distributions of Baseline, Safety and Follow-up data

- In general, the number of observations, mean, median, standard deviation, minimum, and maximum will be calculated for continuous variables. The number of decimal places will be two decimal places.
- Frequencies and percentages will be calculated for categorical data.
- Distribution of continuous variables and proportions of categorical variables will be tabulated by intervention group, and t-test and chi-square tests will be performed to evaluate if these variables are balanced between 2 intervention groups.
- For the primary analysis, baseline is defined as the starting date of Phase 3.

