  - a. We will model the number of gout flares, which can have substantial variation, as Poisson random variables. We will use Poisson regression to compare treatments using a longitudinal repeated measure (PROC GLIMMIX and GENMOD in SAS). Missing data methods will address potential censoring of events among patients who appear to fail to report flares.
  - b. Flare counts will be analyzed separately during Phases 1, 2, and 3 because dose titration during Phase 1 tends to increase the counts, and this effect may still persist in Phase 2, particularly for those still undergoing dose titration; participants are expected to be in steady-state by Phase 3.
  - c. Phase 2 analysis will consider prophylactic treatment after a gout flare and severe side effects of treatment as predictors of subsequent counts.
  - d. During Phase 3 the same set of factors as well as Phase 2 counts will be used to predict gout flare counts. These time-dependent associations will require a mixed effects model using an auto correlated AR(1) variance-covariance to model the series of events.
  - e. For these analyses we may treat the counts as continuous measures in order to introduce more subtle variance-covariance structure and a variety of random effects.
- 7) To determine the patterns of tolerability/toxicity for each treatment during Phase 3 and then overall from weeks 1-72.
  - a. Toxicity events include rises in sUA levels, adverse changes in serum creatinine, CBC, liver function tests (LFTs), blood pressure, and the incidence of skin rashes. The incidence of cardiovascular events of interest will also be included in this analysis.
  - b. Within each Phase we will determine if the incidence of such events differs between treatments. In the Phase 3 analysis baseline covariates will include the summary of toxicity events during Phases 1 and 2 as well as the week 48 sUA level. As in the sixth secondary analysis the same statistical methods for Poisson counts will be used.
  - c. At each clinic visit we will assess the count of each type of major side effect episodes between visits. The analyses will compare treatments using a longitudinal repeated measures analysis with Poisson count, negative binomial counts, and binary outcomes

(PROC GLIMMAX and GENMOD in SAS). Missing data methods will address potential censoring of events among patients who fail to attend clinic visits.

- 8) To describe the effects of baseline covariates and time-dependent covariates on the primary results.

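### Objective 7 names no baseline-adjusted analysis of creatinine, blood counts, ALT or blood pressure, and sets no threshold for the adverse-change events it counts instead

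*SAP*

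**What the plan says.** SAP 5.5, objective 7a, defines the outcomes: "Toxicity events include rises in sUA levels, adverse changes in serum creatinine, CBC, liver function tests (LFTs), blood pressure, and the incidence of skin rashes". Objective 7b sets the comparison, "Within each Phase we will determine if the incidence of such events differs between treatments", and the method: "As in the sixth secondary analysis the same statistical methods for Poisson counts will be used". Objective 7c adds a "longitudinal repeated measures analysis with Poisson count, negative binomial counts, and binary outcomes". Protocol section VIII has the same plan for its seventh secondary objective. Neither document gives a cut-off for an adverse change under this objective.

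The measured values appear in two other places. Protocol section VIII (end of the sample-size text for the primary hypothesis) plans comparisons by treatment on selected variables, laboratory values and vital signs among them: "Simple unadjusted comparisons will apply Student's t-test to continuous variables", with the Wilcoxon test for skewed data. SAP 5.3, whose heading covers baseline, safety and follow-up data, says "t-test and chi-square tests will be performed to evaluate if these variables are balanced between 2 intervention groups".

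Table 5 of the protocol schedules creatinine, CBC, ALT and blood pressure at baseline and at weeks 6, 12, 18, 24, 36, 48, 60 and 72. ALT is the only liver test in that schedule.

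**The concern.** These are numerical series with a baseline value and eight later readings. Scoring each reading as an event or not discards how far it moved. Comparing follow-up means without the baseline value leaves between-person variation in the error term.

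The same SAP section handles its other continuous series differently. Serum urate gets a mixed model in PROC MIXED. Quality of life and tophus area get change from baseline, covariate-adjusted regression and repeated measures. Nothing of this kind is named for the safety laboratory values or blood pressure.

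The protocol background argues at length about whether allopurinol harms or protects the kidney, so a modest average difference in renal function between arms would interest readers. The planned analysis could miss one that the collected data would show.

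Separately, the event counts cannot be computed as written, because nothing says what size of change in "adverse changes in serum creatinine, CBC, liver function tests (LFTs), blood pressure" counts as adverse. A cut chosen late would be discretionary.

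**Working it through.** **1. Sample size.** The documents state no power, SD, correlation or event rate for objective 7. The only stated figure is the primary one in SAP section 4: 90% power with 425 per arm. At a 20% flare rate (variance 0.16) and an 8-point margin, SE = √(2 × 0.16/425) = 0.0274, and power = Φ(0.08/0.0274 − 1.645) = 89.8%. It reproduces. Below I use 950 × 0.9/2 ≈ 427 per arm.

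**2. Assumptions not in the documents.** Normal data; a uniform mean shift; one follow-up visit; baseline-to-follow-up correlation r = 0.6; two-sided 5%. Systolic pressure: SD 15, difference 3 mmHg. eGFR: SD 12, difference 2 ml/min. The event cuts (any worsening; a rise of 20 mmHg; a fall of 10 ml/min) are for illustration only.

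**3. Formulas.** Adjusted SE = SD × √((2/427)(1 − r²)). Unadjusted SE = SD × √(2/427). SD of change = SD × √(2(1 − r)). An event is a change beyond the cut, and its rates are compared as two proportions.

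| | Systolic pressure | eGFR |
|---|---|---|
| Adjusted SE; power | 0.82; 95.5% | 0.66; 86% |
| Unadjusted t-test SE; power | 1.03; 83% | 0.82; 68% |
| SD of change | 13.4 | 10.7 |
| Any worsening: rates; power | 50.0% v 58.8%; 74% | 50.0% v 57.4%; 58% |
| High cut: rates; power | 6.8% v 10.3%; 44% | 17.6% v 22.8%; 48% |

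**4. Range over r = 0.5 to 0.8.**
- Systolic: adjusted 92-99.8%, any rise 64-96%, rise of 20 or more 40-45%, unadjusted 83%.
- eGFR: adjusted 80-98%, any fall 49-86%, fall of 10 or more 42-65%, unadjusted 68%.

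The adjusted analysis leads throughout. At high correlation, scoring any worsening can beat the unadjusted t-test, because a change score uses the baseline.

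**5. Repeated counts, closer to the plan.** In a simulation at 425 per arm (r = 0.5 or 0.7, per-visit event rate 5% or 10%), the shift was set so that analysis of the post-baseline mean, adjusted for baseline, has about 90% power. Robust-variance Poisson counts then reach 31-48% with two visits, as in Phase 3, and 35-58% with eight.

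**6. The opposite case.** If the harm is a jump of 4 SD in 0.5% of one arm and 4% of the other (assumed), Poisson counts have 90-95% power and the adjusted mean comparison 69-76%.

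**7. Why the threshold matters.** If any worsening counted and visits were exchangeable, then with no drug effect the share with at least one event would be 8/9 = 89% over eight visits, 4/5 in Phase 1 (four visits) and 2/3 in each of Phases 2 and 3 (two visits each).

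**The case against.** The strongest reply is that objective 7 is a tolerability analysis, declared exploratory, and that counting adverse changes is a normal way to look for toxicity. Step 6 supports this: for rare, large harms, counts are the better tool. The protocol's own hypersensitivity criteria (an eGFR drop above 50%, ALT above three times the upper limit) describe harm of that kind. This stands, and it is why the counts should be kept.

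A reader might also infer more than the documents support:
- *That the measured values are never compared.* They are, by unadjusted tests under protocol section VIII and SAP 5.3. The latter gives balance as its purpose; the former does not.
- *That baseline adjustment is ruled out.* The protocol lets secondary analyses 2-7 adjust for baseline covariates, which include laboratory values. For objective 7, though, the outcome so adjusted is still the event, not the measurement.
- *That Poisson is the only model.* Negative binomial and binary models are named too.
- *That the laboratory series are collapsed to none versus any.* The protocol sentence "These counts will be coarsened into binary outcomes of no events versus one or more events" sits in a paragraph on counts of major side-effect episodes. It does not name the laboratory or blood pressure series.
- *That the CKD stage 3 quota was set to study change in eGFR.* It serves the secondary objective on flares and tolerability in that subgroup. CKD progression is assigned to the ten-year record follow-up.

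Finally, the SDs, effects and correlations come from outside the documents, and no passage says that any worsening counts as an event. The power figures show direction and rough size only.

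**Conclusion.** The concern holds in a limited form. No baseline-adjusted or repeated-measures analysis of creatinine, blood counts, ALT or blood pressure values is named, and the events analysed under objective 7 have no threshold. If a drug shifts the mean, and under the illustrative assumptions at r = 0.6, baseline adjustment raises power over the planned unadjusted t-test by about 12 points for blood pressure (95.5 − 83) and 18 for eGFR (86 − 68). The gain over single-change event coding is about 21 to 51 points (95.5 − 74; 95.5 − 44) and 28 to 38 points (86 − 58; 86 − 48).

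It would be wrong to conclude that event counts are inferior in general, since the order reverses for rare, large toxicities. The two analyses complement each other. Objective 7 carries no power claim, so no stated figure fails and the primary non-inferiority conclusion is untouched. This is a worthwhile, inexpensive improvement.

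**What to change.** In SAP 5.5, objective 7:

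1. Beside the event analyses, add a PROC MIXED repeated-measures model for each of creatinine/eGFR, ALT (log scale), haemoglobin, white cells, platelets and blood pressure, with the baseline value, arm, visit and arm × visit. State that baseline means week 0, or the screening value where Table 5 allows the test not to be repeated, because SAP 5.3 defines baseline for the primary analysis as the start of Phase 3. Report arm differences with 95% confidence intervals at weeks 24, 48 and 72, labelled exploratory.
2. Write down, before unblinding, the threshold that makes a change in each measure an adverse-change event. Keep the event tables, rash included.

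The cost is SAP wording and a few models in a procedure already planned for objective 2, with no new data. The downside is more output: six measures at three time points give at least 18 further contrasts without multiplicity control, so they should be read as estimates with intervals and not as tests.

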## **6. Data Monitoring Committee Reports**

Data and study progress will be monitored by the study executive committee and by the Data Monitoring Committee. The DMC will review the study progress and safety semiannually with additional meetings and communications as needed.

All reports will be generated in conjunction with the Data Management department using SQL and SAS.

### **6.1. Analytic Sample for DMC Reports**

All subjects randomized more than six weeks prior to the DMC meeting date who initiated intervention (i.e., did not drop out or withdraw prior to start of the allocated intervention) will be included in the analytic cohort for the upcoming DMC report, and all data collected up to four weeks prior to the DMC meeting date will be analyzed. This allows for two weeks lag time for submission of data from sites.

### **6.2. Outline of DMC Reports**

The report is divided into four sections to cover subject disposition, baseline assessment, follow-up assessment, and safety assessment.

#### **Section A: Subject Disposition**

Figure A1. CONSORT Diagram

Figure A2. Overall Study Enrollment

Figure A3. Enrollment by Site  
Table A4. Pre-Screening Log Data.  
Table A5. Protocol Deviations  
Table A6. Terminations  
Table A7. Form Completion, by Form Type  
Table A8. Form Completion, by Site

**Section B: Baseline Assessment**

Table B1. Patient Characteristics  
Table B2. Military Service, VA sites only  
Table B3. Relevant Medical History  
Table B4. Baseline Labs and Assessment  
Table B5. Week 24 Labs and Assessment  
Table B6. Week 48 Labs and Assessment  
Table B7. Study Medication Adherence  
Table B8. Study Medication Dose Change  
Table B9. Concomitant Medications

**Section C: Follow-up Assessment**

[figure not shown]
Table C1. Study Primary Outcome Events  
Table C2. Study Secondary Outcome Events – Part I  
Table C2. Study Secondary Outcome Events – Part II  
Table C2. Study Secondary Outcome Events – Part III  
Table C2. Study Secondary Outcome Events – Part IV  
Table C2. Study Secondary Outcome Events – Part V

**Section D: Safety Assessment**

Table D1. Rates of Non-Serious Adverse Events (NAEs) and Serious Adverse Events (SAEs), by Site  
Table D2. Summary of Non-Serious Adverse Events  
Table D3. Summary of Serious Adverse Events  
Table D4. Non-Serious Adverse Events by System Organ Class and Preferred Term  
Table D5. Serious Adverse Events by System Organ Class and Preferred Term

7. Shell DMC Tables (subject to change)

Figure A1. CONSORT Diagram

**Table A4. Pre-Screening Log Data.**

Reason Why no tEnrolled	Eligible but did not enroll (N= )	%	Cumulative %
A. Refusal	N	%	%
B. Provider decision	N	%	%
C. Dual Enrollment Issue	N	%	%
D. Missing – No reason given	N	%	100%

**Table A5. Protocol Deviations**

Description of Protocol Deviation	Sample (N= )	Form Location	Element Codes
Informed consent and/or HIPAA authorization not signed until after study procedures started	N (%)	PD	DVDECOD=1
Eligibility criteria violated	N (%)	PD	DVDECOD=2
Allopurinol/Febuxostat not prescribed and/or not dispensed as per protocol	N (%)	PD	DVDECOD=3
Required study procedure not completed	N (%)	PD	DVDECOD=4
SAE not reported per protocol	N (%)	PD	DVDECOD=5
Lab blood draws not obtained as per protocol	N (%)	PD	DVDECOD=6
Participant took Probenecid and or/ Lesinurad	N (%)	PD	DVDECOD=7
Participant took other excluded medication after randomization	N (%)	PD	DVDECOD=8
Required source documentation could not be obtained	N (%)	PD	DVDECOD=9
Patient seen outside visit window (Study visits will have a window +/- 1 week in Phase 1 and +/- 2 weeks in Phase 2 and 3)	N (%)	PD	DVDECOD=10
Other protocol deviation 	N (%)	PD	DVDECOD=11

See Appendix B.

**Table A6. Early Terminations**

Reason for Termination	Sample (N= )	Form Location	Element Codes
Death	N (%)	EOS	DSDECOD=1
Side effects with study medications	N (%)	EOS	DSDECOD=2
Provider decision	N (%)	EOS	DSDECOD=3
Participant decision	N (%)	EOS	DSDECOD=4
Participant lost to follow-up	N (%)	EOS	DSDECOD=5
Study site closure	N (%)	EOS	DSDECOD=6
Participant required to take exclusion medication on a regular basis	N (%)	EOS	DSDECOD=7
Other reasons for early termination	N (%)	EOS	DSDECOD=8

See Appendix C.

